9.2.2.1 SPEP, UPEP, SFLC, SIFE, and UIFE

Serum protein electrophoresis, UPEP, SIFE, UIFE, and SFLC will all be conducted at the local laboratory. Samples will be collected every 28 ± 7 days (starting from cycle 1 day 1) irrespective of cycle duration including dose delays and treatment discontinuation. Blood will be obtained for SFLC, SPEP, and SIFE. Twenty-four-hour urine samples will be obtained for UPEP and UIFE. Results for SPEP, UPEP, or SFLC must be available at screening and before enrollment. Serum protein electrophoresis, UPEP, and SFLC will be repeated on cycle 1 day 1 (unless screening values are within 14 days of cycle 1 day 1). Post cycle 1 day 1, UPEP and UIFE will be measured every disease assessment as well as SPEP and SIFE. Subjects with IgA, IgD, or IgE myeloma must have a quantitative IgA, IgD, or IgE (as appropriate) with each response assessment.

Subjects will be evaluated for disease response and progression according to the IMWG response criteria in Section 12.11 (Kumar et al, 2016). Disease status categories include sCR, CR, VGPR, PR, SD, and PD.

The following confirmation assessments are required for all response categories (sCR, CR, VGPR, PR, and progression*); refer to definitions in Section 12.11):

* Every effort should be made to obtain 2 consecutive samples at any time prior to initiation of any new therapy. If not possible to obtain the second consecutive assessment to confirm disease progression before initiation of any new therapy, this confirmatory sample for disease progression may be obtained after the new therapy is initiated.

- all response categories require 2 consecutive assessments made at any time before initiation of any new therapy
- all categories other than progression also require no known evidence of progression including new bone lesions if radiographic studies were performed
- confirmation of CR or better requires bone marrow assessment (aspirate or biopsy per IMWG-URC guidelines)

- extramedullary plasmacytoma evaluation (if present at screening)
- a second assessment is not required for radiographic and bone marrow assessments

Disease parameters needed to determine disease response, progression, and IRC adjudication will be collected via patient eCRFs and reviewed by the IRC.

9.2.2.2 Bone Marrow Sample Evaluation Including FISH and MRD[-]CR Assessment

A baseline bone marrow aspirate sample will be collected at screening, or prior to dosing at cycle 1 day 1. A bone marrow sample obtained as standard of care may be used as the baseline sample if taken within 45 days prior to enrollment for FISH and MRD testing. The first sample obtained for baseline bone marrow aspirate will be for tumor specific sequence identification for MRD measurement by next-generation sequencing (NGS) at the central lab.

After screening, bone marrow aspirate will be obtained:

- at time of suspected CR or better. Depending on when this procedure occurs, an additional aliquot of bone marrow aspirate will be frozen and saved at the central lab for MRD testing to be performed at a later time.
- at time of MRD assessment. MRD will be conducted in subjects with suspected CR or better at 12 months (\pm 4 weeks) but may be performed as early as 8 months after start of treatment in subjects with suspected CR or better. Subjects with a MRD[-]CR response at the first time point should have the subsequent MRD assessment 12 months \pm 4 weeks after the earlier assessment, if subjects have not relapsed nor started new antimyeloma therapy prior to this subsequent MRD assessment.

If the bone marrow aspirate sample taken is found to be of insufficient quantity or quality for testing, the site may be contacted to request provision of a suitable archival bone marrow aspirate sample.

9.2.2.3 Bone Lesion Assessment (Skeletal Survey, Computed Tomography [CT], or Positron Emission Tomography/CT [PET/CT])

Skeletal survey will include lateral radiograph of the skull, anteroposterior and lateral views of the spine, and anteroposterior views of the pelvis, ribs, femora, and humeri. Low-dose whole body computed tomography or fluorodeoxyglucose-positron emission tomography/computed tomography (FDG-PET/CT) may be used in place of skeletal survey. Bone lesion assessment at screening (all subjects) may be done within 28 days prior to enrollment, if performed as a part of standard of care. It should be repeated if worsening clinical symptoms suggest PD or as clinically indicated. The same method of

assessment used at baseline will be used throughout the study. These imaging studies will be read locally.

9.2.2.4 Quantitative Immunoglobulin

Quantitative immunoglobulins IgG, IgM, and IgA will be performed at screening for all subjects. If IgD or IgE type of myeloma, IgD or IgE will be performed as well.

After screening, quantitative IgA, IgD, and IgE will be assessed every 28 days (± 7 days) in subjects with IgA, IgD, or IgE myeloma, respectively.

Quantitative immunoglobulins (IgG, IgM, IgA) will be repeated every 12 months ± 2 weeks from cycle 1 day 1 in subjects with PR or better, or if applicable, may be done at time of MRD assessment. Immunoglobulins may also be obtained more frequently as clinically indicated.

9.2.2.5 Extramedullary Plasmacytoma

Extramedullary plasmacytoma evaluation will be conducted at screening only if a lesion is suspected clinically. The evaluation may be done within 28 days prior to enrollment, if performed as a part of standard of care. If a measurable extramedullary plasmacytoma is detected during screening, evaluation will be repeated during treatment to confirm a response of PR or better, or to confirm PD, or as clinically indicated. Plasmacytomas identified by physical examination during screening should be monitored by physical examination locally every 28 (± 7) days until undetectable and then as clinically indicated. If assessment can only be performed radiologically, then evaluation of extramedullary plasmacytomas should be done every 12 weeks ± 2 weeks until a plateau or CR. Radiographical assessment may be done as clinically indicated and at the time of suspected disease progression. The same technique, which may include clinical evaluation by palpation, ultrasound, CT scan, magnetic resonance imaging (MRI), or positron emission tomography/computed tomography (PET/CT) should be employed for each measurement of plasmacytoma dimensions as clinically appropriate (refer to Section 12.11). Bidimensional lesion measurements must be performed and recorded in the designated eCRF.

9.2.2.6 Progressive Disease Assessment

Confirmation of PD requires 2 consecutive assessments made at any time before the initiation of any new therapy*, as well as no known evidence of progressive or new bone lesions if radiographic studies were performed. Radiographic studies are not required to

satisfy these response requirements. Bone marrow, plasmacytoma, and skeletal survey assessments are not required to be confirmed by repeat testing.

* Every effort should be made to obtain 2 consecutive samples at any time prior to initiation of any new therapy. If not possible to obtain the second consecutive assessment to confirm disease progression before initiation of any new therapy, this confirmatory sample for disease progression may be obtained after the new therapy is initiated.

The assessments outlined in Section 12.11 are required for PD. Subjects will be considered to have PD if they meet the criteria for progression by a variable that was not considered measurable at baseline; however, for subjects who had a measurable serum or urine M-spike at baseline, progression cannot be defined by increases in SFLC alone (Kumar et al, 2016).

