9.2.2 Efficacy Assessments

Disease assessments will be based on local laboratory data and local imaging obtained in accordance with the IMWG-Uniform Response Criteria (IMWG-URC) (Section 12.11) until confirmed PD (Section 9.2.2.6) irrespective of cycle duration including dose delays and treatment discontinuation as indicated in the Schedule of Activities (Table 2-1).

After discontinuation from study treatment, subjects who do not have confirmed PD are required to continue disease response assessments and report new antimyeloma

treatment and will be followed every 28 ± 7 days until first subsequent antimyeloma treatment, death, loss to follow-up, withdrawal of full consent, confirmed PD, or end of study, whichever comes first.

Disease response and progression assessments include: serum and urine protein electrophoresis (SPEP, urine protein electrophoresis [UPEP], respectively), SFLC, serum and urine immunofixation (SIFE, UIFE, respectively) (Section 9.2.2.1), quantitative IgA, IgD, or IgE (for subjects with IgA/IgD/IgE myeloma), bone marrow sample evaluation (Section 9.2.2.2), serum calcium, bone lesion assessment (Section 9.2.2.3) and extramedullary plasmacytoma evaluation (Section 9.2.2.5).

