PD	
 Increase of 25% from lowest confirmed response value in 1 or more of the following: 
 Serum M-component (absolute increase must be ≥ 0.5 g/dL if the lowest M-component was < 5 g/dL) Urine M-component (absolute increase must be ≥ 200 mg per 24 hours) Only in subjects without measurable serum and urine M protein levels: the difference between involved and uninvolved FLC levels (absolute increase must be > 10 mg/dL) Increase of serum M-component of ≥ 1 g/dL if the lowest M-component was ≥ 5 g/dL Appearance of new lesion(s), $\geq 50\%$ increase from nadir in SPD of > 1 lesion, or $\geq 50\%$ increase in longest diameter of a previous lesion > 1 cm in short axis $\geq 50\%$ increase in circulating plasma cells (minimum of 200 cells per μL) if this is the only measure of disease

Page 2 of 2

CR = complete response; FC = flow cytometry; FLC = free light chain; PD = progressive disease; PR = partial response; sCR = stringent complete response; SFLC = serum-free light chain; SPD = maximal perpendicular diameter; VGPR = very good partial response

All response categories (complete response [CR], stringent complete response [sCR], very good partial response [VGPR], PR) require 2 consecutive assessments made at any time before the initiation of any new therapy, as well as no known evidence of progressive or new bone lesions if radiographic studies were performed. Radiographic studies are not required to satisfy these response requirements. Bone marrow, plasmacytoma, and skeletal survey assessments are not required to be confirmed by repeat testing.

For sCR: presence/absence of clonal cells is based upon the kappa/lambda (κ/λ) ratio in aspirate. "Measurable" disease is defined by at least 1 of serum protein electrophoresis (SPEP) ≥ 0.5 g/dL, urine protein electrophoresis (UPEP) ≥ 200 mg per 24 hours, or in subjects without measurable serum or urine M-protein, serum free light chains (SFLC) > 100 mg/L (involved light chain) and an abnormal SFLC κ/λ ratio.

Determination of PD while on study requires 2 consecutive assessments made at any time before classification of PD and/or the institution of new therapy*. Serum M-component increases of ≥ 1 g/dL from nadir are sufficient to define progression if nadir M-component is ≥ 5 g/dL.

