
Number of doses of pomalidomide administered

It is defined as the total number of non-zero doses of pomalidomide a subject received during the treatment period of the study

Number of doses of dexamethasone administered

It is defined as the total number of non-zero doses of dexamethasone a subject received during the treatment period of the study

Overall Response (OR)

OR is the best overall confirmed response of partial response (PR), very good partial response (VGPR), complete response (CR), or stringent complete response (sCR).

Overall Response Rate (ORR)

Overall Response Rate (ORR) is defined as the proportion of subjects that reach the overall response among all subjects who received at least 1 dose of the carfilzomib.

Overall Survival (OS)

OS is defined as time from start of treatment until death from any cause.

$OS = (\text{Death date or date of censoring if censored} - \text{start of any study treatment date} + 1) / 30.4$

Subjects still alive will be censored at the date last known to be alive. If the date last known to be alive is after the date that triggers the analysis (ie, the data cutoff date), the subject will be censored at the analysis trigger date.

Progression Free Survival (PFS)

PFS is defined as the time from the first dose date of any study treatment until the first documentation of disease progression or death due to any cause, whichever occurs first in the absence of subsequent anticancer therapy and if not > 70 days from the last non-NE, post-baseline disease assessment. PFS will be censored at the last non-NE, post-baseline disease assessment or the earlier of the following, where applicable: (a) the last non-NE, post-baseline disease assessment prior to subsequent anticancer therapy, or (b) the last non-NE, post-baseline assessment followed > 70 days later by disease progression or death; otherwise, at first dose date. Disease progression is based on the IMWG-URC [2016].

PFS time in months= [(PD or death date, whichever occurs first) or date of censoring if censored– start of treatment date + 1] / 30.4.

Table 5-1. Conventions for Censoring for PFS

Situation	Date of Progression or Censoring	Outcome
No PD or death, no new anticancer treatment	Last visit; otherwise, first dose date of any study treatment	Censored
No PD or death, new anticancer treatment	Last visit prior to new treatment; otherwise, first dose date of any study treatment	Censored

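### Protocol Section 9.2.2.6 makes absence of new or progressive bone lesions a condition for confirming progression, contradicting Section 9.2.2.1 and Appendix 11

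*Protocol*

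**What the plan says.** Three places in the protocol state how a disease category is confirmed.

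- **Section 9.2.2.6 (Progressive Disease Assessment).** Confirmation of PD needs two consecutive assessments before any new therapy, "as well as no known evidence of progressive or new bone lesions if radiographic studies were performed". The next sentence reads "Radiographic studies are not required to satisfy these response requirements". The section later adds: "The assessments outlined in Section 12.11 are required for PD".
- **Section 9.2.2.1 (confirmation bullets).** Two consecutive assessments are needed for every category. Then: "all categories other than progression also require no known evidence of progression including new bone lesions if radiographic studies were performed".
- **Section 12.11 (Appendix 11, notes under the criteria table).** The bone-lesion condition follows a list naming CR, sCR, VGPR and PR. PD has its own rule: "Determination of PD while on study requires 2 consecutive assessments made at any time before classification of PD and/or the institution of new therapy". That rule carries no bone condition.

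Section 9.2.2 runs disease assessments until PD is confirmed and cites Section 9.2.2.6 by number. In the SAP, Section 5 bases progression for PFS on the 2016 IMWG criteria. Table 9-2 makes the IRC reading primary for PFS and duration of response, with investigator and ORCA readings as sensitivity analyses.

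**The concern.** The clause works in the wrong direction. New or progressive bone lesions count against a response, so requiring their absence makes sense when a response is being confirmed. Requiring their absence before progression can be confirmed means that further evidence of progression blocks the finding of progression.

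A site that applied the sentence as written could leave a progression with bone involvement unconfirmed. If the subject then started new therapy, SAP Table 5-1 would censor PFS at the last evaluable visit before that therapy, and duration of response follows the same censoring rules. A true progression would then be recorded as a censored observation, and that censoring would be informative. Both endpoints would look longer than they are.

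**Working it through.** **Comparison of the passages**

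| Place | Category confirmed | Two consecutive assessments | No new or progressive bone lesions |
|---|---|---|---|
| 9.2.2.6 | PD | required | required, if imaging was done |
| 9.2.2.1 | sCR, CR, VGPR, PR | required | required, if imaging was done |
| 9.2.2.1 | progression | required | expressly not applied |
| 12.11 | CR, sCR, VGPR, PR | required | required, if imaging was done |
| 12.11 | PD | required | not stated |

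Section 9.2.2.6 is the only place that applies the bone condition to PD.

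**Test case.** Take a subject with two consecutive M-protein rises that meet the Appendix 11 thresholds, and a new bone lesion on imaging.

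- Under 12.11, PD is met.
- Under 9.2.2.1, nothing blocks it, because progression is exempt.
- Under 9.2.2.6 read literally, PD cannot be confirmed.

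**Likely origin (an inference).** The sentence after the clause speaks of response requirements under a heading about progression. It matches the response paragraph of Appendix 11, as does the sentence after that on repeat testing. Response text appears to have been carried over with PD as its subject.

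**Scale of one misclassified progression.** The plan gives no figure to reproduce. The only document input is 52 treated subjects (Protocol Section 10.1). The number of events before the time point, k, is an assumption, varied from 15 to 30. No other censoring is assumed.

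With all k events counted, the Kaplan-Meier estimate is S = (52 − k)/52. Recording the event at rank r as censored removes the factor (52 − r)/(52 − r + 1), so the estimate rises by S/(52 − r). The rise is smallest at r = 1 and largest at r = k, where it equals 1/52.

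| k | S | Rise at r = 1, S/51 | Rise at r = k, S/(52 − k) |
|---|---|---|---|
| 15 | 37/52 = 0.712 | 1.40 points | 1.92 points |
| 20 | 32/52 = 0.615 | 1.21 points | 1.92 points |
| 25 | 27/52 = 0.519 | 1.02 points | 1.92 points |
| 30 | 22/52 = 0.423 | 0.83 points | 1.92 points |

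One subject therefore moves a later PFS estimate by 0.8 to 1.9 points under these assumptions.

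**The case against.** The best case against is that this is an editorial slip which corrects itself.

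- **The section sends the reader to Appendix 11 for PD.** It does, but that instruction adds the Appendix 11 assessments. It does not withdraw the clause, so the site is left with two rules that disagree.
- **Skeletal survey, plasmacytoma and marrow findings need no repeat testing, and Section 9.2.2.3 repeats bone imaging when symptoms suggest PD.** Both are true, and both make the literal reading less natural. Neither removes the stated condition from the PD sentence.
- **The primary PFS and duration-of-response analyses use the IRC.** This largely stands. Section 5.1 has the IRC review the disease data without knowledge of the investigator's assessments. The clause would reach the IRC or ORCA results only if the charter or algorithm repeats it, and the documents do not show that.
- **The Appendix 11 criterion on new lesions may concern plasmacytomas.** This is a fair point: it sits with lesion-diameter rules, and similar wording recurs in the plasmacytoma note. The contradiction does not need it, because the exemption in 9.2.2.1 and the separate PD rule in 12.11 are enough.
- **The Kaplan-Meier figures are generic.** This also stands. They show what one subject is worth, not how many are affected, which could be none. The 1/52 ceiling also needs the absence of other censoring. SAP Table 5-1 plans for censoring, and a smaller risk set can make one event's step larger.

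**Conclusion.** The concern holds. The PD sentence in Section 9.2.2.6 is wrong as written and conflicts with two other current passages. Because Section 9.2.2 sends sites to that section by number, it is an operative instruction.

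The demonstrable consequence is narrow: a possible upward bias in the investigator-assessed sensitivity analyses of PFS and duration of response, which are secondary and descriptive. Its size is unknown. The 0.8 to 1.9 points per affected subject rests on 52 subjects, an assumed 15 to 30 events and no other censoring. Nothing in the documents shows that any site has applied the clause literally. ORR, MRD[-]CR and the powers in Table 10-1 do not depend on it.

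It should still be fixed. Enrollment has stopped, but Section 9.1.4.1.1 places end-of-study visits 4 years after the last enrollment and a final analysis is planned, so progressions may still need to be confirmed.

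**What to change.** 1. In Section 9.2.2.6, delete the bone-lesion clause from the sentence on confirming PD, so that the condition attaches to response categories only, as in Sections 9.2.2.1 and 12.11.
2. Align the following sentence, which refers to response requirements, with a section about progression.
3. Check that neither the IRC charter nor the ORCA specification contains the same clause.

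No new PD criterion is needed; Appendix 11 remains the reference.

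**Cost.** The text change is one clause plus one aligned sentence, with two document checks. As a protocol change it also needs IRB/IEC submission and, where necessary, approval (Section 12.3), across approximately 45 planned sites (Section 5.2.2). No data collection or analysis method changes.

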9.2.3 Safety Assessments

Planned time points for all safety assessments are listed in the Schedule of Activities see (Table 2-1).

9.2.4 Adverse Events and Serious Adverse Events

The method of recording, evaluating, and assessing causality of adverse events, and serious adverse events and the procedures for completing and transmitting serious adverse event reports are provided in Section 12.4.

9.2.4.1 Time Period and Frequency for Collecting and Reporting Safety Event Information

9.2.4.1.1 Adverse Events

The adverse event grading scale to be used for this study will be the Common Terminology Criteria for Adverse Events (CTCAE) version 5 and is described in Section 12.4.

The investigator is responsible for ensuring that all adverse events observed by the investigator or reported by the subject that occur after signing of the informed consent through 30 days after the last dose of study drugs (carfilzomib, pomalidomide, and dexamethasone) are reported using the Events CRF.

9.2.4.1.2 Serious Adverse Events

The investigator is responsible for ensuring that all serious adverse events observed by the investigator or reported by the subject that occur after signing of the informed consent through the end of long-term follow-up or 30 days after the last dose of study drugs (carfilzomib, pomalidomide, and dexamethasone), whichever comes later, are reported using the Events CRF.

All serious adverse events will be collected, recorded and reported to the sponsor or designee within 24 hours of the investigator's awareness of the event, as indicated in Section 12.4. The investigator will submit any updated serious adverse event data to the sponsor within 24 hours of it being available.

Since the criteria in the CTCAE grading scale differs from the regulatory criteria for serious adverse events, if adverse events correspond to grade 4 CTCAE toxicity grading scale criteria (eg, laboratory abnormality reported as grade 4 without manifestation of life-threatening status), it will be left to the investigator's judgment to also report these abnormalities as serious adverse events. For any adverse event that applies to this situation, comprehensive documentation of the event's severity must be recorded in the subject medical records.

9.2.4.1.3 Serious Adverse Events After the Protocol-required Reporting Period

There is no requirement to monitor study subjects for serious adverse events following the protocol-required reporting period (as defined in Section 9.2.4.1.2) or after end of study. However, these serious adverse events should be reported to Amgen (regardless of causality) if the investigator becomes aware of them. Per local requirements in some countries, investigators are required to report serious adverse events that they become aware of after end of study. If serious adverse events are reported, the investigator is to report them to Amgen within 24 hours following the investigator's awareness of the event.

Serious adverse events reported outside of the protocol-required reporting period will be captured within the safety database as clinical trial cases and handled accordingly based on relationship to investigational product. **If further safety related data is needed to fulfill any regulatory reporting requirements for a reportable event, then additional information may need to be collected from the subject's records after the subject ends the study.**

